Scientific Title

- Image analysis with artificial intelligence to increase precision in breast cancer screening, the ScreenTrust MRI substudy: a prospective trial of AI to select women for supplemental MRI in breast cancer screening

Countries of Recruitment

- Sweden

Health Condition or Problem Studied

- Breast cancer

Intervention

- Intervention Name: Artificial intelligence-based framework to select for MRI (AI MRI)

- Intervention Description: An AI-based framework has been developed by researchers at Karolinska Institute (led by [name]) and Royal Institute of Technology (led by Dr: [name]). The specific AI-implementation (AI tool) in this study is a result of AI predictions from three equally weighted component AI models analyzing mammograms: (i) masking predictor, (ii) risk predictor and (iii) cancer signs predictor (by one commercial CAD model and one in-house academic CAD model); the age of the woman is also taken into account by multiplying the score with (110-age)/70. The purpose of the age factor is to attain a relatively similar proportion of MRI exams in the lower and higher age groups. The aim of the AI tool is to identify women with the highest probability of having a delay in cancer detection, i.e., having had a false negative screening mammogram. The specific AI tool and its settings will remain the same during the study. For each examination, the AI tool will produce an AI Joint Score and an AI Masking Score. The AI Masking Score cut-off point was defined by the median of examinations collected during the initial period of March 1 to March 24, 2021. The cut-off point of the AI Joint Score was defined by the 92nd percentile of the initial population. Women meeting these criteria will be invited to the study, and randomized to MRI or no-MRI (standard-of-care).

Key Inclusion and Exclusion Criteria

All women attending screening mammography at Karolinska University Hospital will be included in the study. The ethical review authority has waived the need to obtain individual written informed consent to be included in this initial stage of the study. However, for women that will be invited to undergo MRI, a written informed consent will be collected.

- Inclusion criterion

- women for whom a standard four-view mammography examination was acquired at regular screening (right MLO, right CC, left MLO, left CC; exam code 66200)

- Exclusion criteria:

- women attending screening as part of a surveillance program (i.e, referred due to high risk of breast cancer, or a personal history of breast cancer) - defined by having an exam code different from regular screening

- women having breast implant(s)
- women recalled for diagnostic work-up in the current regular screening process

- women whose exams the AI tool cannot process (e.g., corrupt file structures, irregular file paths, missing dicom tags describing window center, window width, image laterality, patient age, pixel array)

Study Type

Type of Study: Randomized clinical trial

Study design: All women with negative screening mammograms less than one month before the selection day will be analyzed for MRI eligibility. We will exclude women who participate in special surveillance programs, who have breast implants, who had prior breast cancer, who have breast implant, who are breast feeding or have any MRI contraindication requiring radiologist assessment. Then AI scores will be calculated as described above (Intervention). The workflow for the study until randomization is described in **Figure 1**. The number of women randomized to the MRI-group and the non-MRI group will be adapted to available MRI capacity over time.

[figure not shown]

Figure 1. Study flow chart until Randomization.

Regular contraindications for MRI will apply. A Signa Premier 3T MRI scanner from GE Healthcare will be used. The MRI protocol will contain a T2-weighted Dixon sequence and a T1-weighted dynamic contrast enhanced series, and will remain the same through the course of the study. All MRI exams will be assessed by two radiologists, where the second reader will have access to the assessment of the first reader. In case of disagreement, a consensus discussion between two radiologists will be held. The MRI exams will be assessed according to BI-RADS, and follow-up will depend on the BI-RADS category (see **Figure 2**).

Follow-up of breast cancer status and tumor characteristics will continue until, and including, the next planned screening examination (within 27 months of the first included screening examination).

[figure not shown]

Figure 2. Study flowchart for women undergoing MRI. Number of weekly exams for each category are prior estimates based on the DENSE trial.

Date of First Enrollment

Study start is estimated to take place in April 1, 2021.

Sample Size

The study shall enroll study persons until 1000 women have undergone MRI scanning. With an 95% attendance rate after invitation to MRI, we estimate that around 1050 women have been invited for MRI (and thus included in the MRI group). Given the variable randomization ratio, described above, we estimate that a slightly larger number of women have been included in the non-MRI group.

AMENDMENT IN MARCH 2023: Due to a decision to cease to invite women after May 2023, the sample size of 1000 performed MRI exams will not be attainable. An assessment of MRIs revealed a

higher cancer detection rate than we had anticipated, which should results in a bigger effect size than we had assumed in our sample size calculations for the study. Thus, we believe that the statistical power in the trial will be similar to what we had originally anticipated, even with the smaller number of participants. See also "completion date" below as well as the section about sample size calculations in the SAP.

Recruitment Status

Active

Primary Outcome(s)

The primary outcome is a composite endpoint representing **early detection failure** – a breast cancer diagnosed with any of the below characteristics:

- Interval cancer
- Cancer with invasive component larger than 15 mm
- Cancer with lymph node metastasis

The follow-up time starts once the initial mammography and screening MRI are fully processed and any cancer detected at the initial examination has been diagnosed. Thus, the cancers that will be considered for primary outcome are the women that are healthy after the initial examination. A positive primary outcome will be based on interval cancers and the cancers that are screen-detected during a 27-month follow-up time after initial screening and fulfil the above criteria.

Secondary Outcome(s)

To the extent that a secondary outcome measure does not overlap with the primary outcome, it may be included in interim reporting.

1. Women invited, women declined and women accepted to participate; including reason for non-participation (contraindication, patient choice, no response).

2. Distribution of AI scores for: i) Joint model, ii) AI risk score, iii) AI masking score, iv) AI CAD score(s).

3. a) Breast cancer diagnosed by screening MRI.

b) All breast cancers diagnosed during the study time including the initial screening, including mode of detection (MRI, mammographic detection, clinical detection including time since screening) for all women for whom AI scores were calculated (above and below threshold)

For all cancers in the outcome measures, the following tumor characteristics will be reported:

- a) Invasiveness (in situ or invasive; micro-invasive counted as in situ)
- b) Histology (ductal, lobular, mucinous, tubular, other)
- c) Lymph node status (0, 1-3, or more than 4 lymph node metastases)
- d) Tumor size (in mm) in situ and invasive component separately measured by pathologist
- e) Ki-67 percent. With a 20% binary cut-off, and an ex 14% cut-off level

d) Molecular subtype (Luminal A-like defined as estrogen and/or progesterone receptor positive and HER2 negative and KI-67 <14%, Luminal B-like defined as estrogen and/or progesterone receptor positive and HER2 positive/negative and KI-67 >=14%, HER2-positive defined as estrogen and progesterone receptor negative and HER2 positive, and

Triple negative defined as estrogen and progesterone receptor and HER2 negative)

4. Radiological process measures: distribution of BI-RADS scores (amount of fibroglandular tissue, background parenchymal enhancement, and any lesion); number and outcome of second look ultrasound, biopsies, short-term MRI follow-up. We will report operational characteristics of the screening MRI (cancer detection rate, recall rate, positive predictive value for 2nd look ultrasound decision and for biopsy decision).

5. Questionnaire for women undergoing MRI: self-examination habit (yes, sometimes, often); previous MRI (yes, no); prior breast cancer (yes, no, which breast and year); prior non-malignant breast disease (yes, no, which year); first-degree relative with breast cancer (yes, no, at what earliest age); first-degree relative with ovarian cancer (yes, no, earliest age); Age of menarche, Parity, Age of first pregnancy, Number of children born, Time of breast-feeding, date of latest menstruation; reason for no menstruation, use of hormonal medications; use of Cozaar or Losartan; Current length and weight. They may also fill in a questionnaire concerning their experience of undergoing a screening MRI.

Explorative: The influence on cancer incidence and detection of the following potential predictors or modifiers will be explored (further detailed in the Statistical Analysis Plan): Radiologist assessments of screening mammogram at inclusion, Age, Density, AI scores: Overall pipeline (the basis for cut-off point), and various cut-off points for each of the three AI components (risk, masking and CAD).

Ethics Review

Approved on April 28, 2020, with registration id EPM 2020-00487 by the Ethical Review Authority of Sweden (email: [contact], [contact]).

Completion date

Patient invitations to the study will cease in May 2023, even if we do not reach the original target of 1,000 performed MRI exams. The reason is that there is an increasing risk that the same women that were included in April 2021 will return for their next round of regular screening. Having a second round for some women and not for others would be inconsistent and we have decided to avoid this situation. See also "Sample size" above.

Summary Results

N/A

IPD sharing statement

We plan to share individual participant-level data to the extent that the data can be considered anonymous by the responsible research body. A transfer agreement for academic research purposes will be required.

SPIRIT-AI additional items

Protocol Version

1.0, March 10, 2020.

Funding

See WHO above.

Roles and responsibilities

Protocol contributors

[name] PhD, Karolinska University Hospital: Principal Investigator, Radiology team leader

[name], Karolinska Institutet: Biostatistician

[name], SciLife Lab / Royal School of Engineering, Stockholm: Computer science team leader

[name], Division of Robotics, Perception and Learning, Royal School of Engineering

Trial sponsor:

See WHO above.

Role of study sponsor and funders

The primary sponsor of the study, Karolinska University Hospital, represented by the PI is responsible for collection and management of the study; for study design, analysis and interpretation of data, writing of the report, and the decision to submit the report for publication (the PI will have ultimate authority to decide over these activities). The funding has been provided by regional authorities and the breast cancer patient organization, which will have no influence over study management.

Composition, roles and responsibilities of steering committee

The steering committee consists of (all from Karolinska University Hospital, except for [name] from SciLifeLab/KTH and [name] from Karolinska Institute): [name], PI; [name], computer science team leader; [name], biostatistics; [name], head of breast radiology; [name], breast surgeon; [name], breast surgeon; [name], breast oncologist.

Introduction

Background and rationale

Breast cancer is the most common cancer for women. Though the patients have a relatively good probability of survival, around 1500 women die each year in Sweden from the disease. Mammographic screening has been shown to lower mortality by around 30 (1). However, in the screening programs large resources are consumed and around 30 percent of cancers go undetected and the women find them by noticing a lump in the breast (2). MRI has consistently been shown to have a higher sensitivity than mammography, but often a lower specificity. MRI is also several times more expensive than mammography, and there is limited capacity for additional examinations in the current installations. Thus, even if MRI would increase early cancer detection, it would be offered only to a limited group of women. In a Dutch study, MRI was offered to women at average risk but extremely high mammographic density. The

researchers found that the additional cancer detection rate was 16.5 per 1000 MRI screenings (compared to around 5 per 1000 mammography screenings in the general population) (3). For women undergoing MRI they found a decrease from 5.0 interval cancers / 1000 women to 0.8 interval cancers / 1000 women; as well as a decrease in the lymph node positivity from 45% to 15%. Since 2018 our group, together with collaborators, has developed AI-based tools that in retrospective analysis seems to offer higher precision for short-term breast cancer risk prediction than using mammographic density (4). In this prospective clinical study, we will examine how using an AI pipeline to select women who are invited for MRI will affect the number of screen-detected cancers and the number of cancers with poor prognosis shown by lymph node positivity and/or interval cancer detection.

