5.4 Primary analyses: Superiority

Superiority analyses in terms of the absolute incidence of the primary CEP (significantly delayed cancer detection) further defined in the primary end-point (4.1). The study has been powered for the primary analysis of difference in CEP between the MRI and the no-MRI (standard of care) arms of the study.

Analyses will compare the difference CEP between study arms. This can be done on an absolute or a relative scale. The primary analysis will be performed on an absolute scale and supportive analyses may use a relative scale.

Absolute scale. The absolute difference in CEP is defined as the CEP the standard arm minus the CEP in the experimental arm (Δ CEP = CEP_{Std}- CEP_{Exp}) or vice versa, as appropriate. It is estimated by plugging into the formula the observed proportions. An approximate 100(1-a)% two-sided Wald confidence interval for Δ CEP is calculated as

$$\widehat{\Delta CEP} \pm z_{\alpha/2} \sqrt{\frac{\widehat{CEP}_{Exp} * (1 - \widehat{CEP}_{Exp})}{n_{Exp}} + \frac{\widehat{CEP}_{Std} * (1 - \widehat{CEP}_{Std})}{n_{Std}}}.$$

Relative scale. The relative difference in CEP is defined as the CEP in the experimental arm divided by the CEP in the standard arm (rCEP = CEP_{Exp}/CEP_{Std}) or vice versa, as appropriate.

It is estimated by plugging into the formula the observed proportions. An approximate 100(1-a)% two-sided Wald confidence interval for rCEP is calculated as

$$exp\left(log(r\widehat{CEP}) \pm z_{\alpha/2}\sqrt{\frac{1}{\widehat{CEP}_{Exp}*n_{Exp}} - \frac{1}{n_{Exp}} + \frac{1}{\widehat{CEP}_{Std}*n_{Std}} - \frac{1}{n_{Std}}}\right)$$

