5.5 Secondary analyses

5.5.1. We will calculate summary statistics for the age and number of women not eligible for MRI, eligible and invited for MRI, women declined MRI and women undergoing MRI; including reason for non-participation (contraindication, patient choice, no response): for the entire study period, and how it changes over time.

5.5.2. We will calculate summary statistics and graphically show the distribution of AI scores for: i) Joint model, ii) AI risk score, iii) AI masking score, iv) AI CAD score(s). We will subgroup these analysis by age group at the time of initial screening: 40-49, 50-59, 60-69 and 70-74 years. We will subgroup these analysis by participation category (eligible vs. not eligible for MRI, invited vs. not invited for MRI, eligible women undergoing vs. not undergoing MRI, declined MRI (by reason)).

5.5.3. a) For women invited to MRI, we will calculate the number and proportion of breast cancer diagnosed by screening MRI, and perform logistic regression analysis to examine associations with AI scores (joint and component scores), age of the woman, by responses in the study persion questionnaire (see section 4.2.5), by BI-RADS scores of amount of fibgroglandular tissue and background parenchymal enhancement. Similar analysis will be carried out for all cancers diagnosed during the study time. We will repeat the analyses for women actually undergoing MRI.

b) We will perform similar analyses as above for all women undergoing mammography only, but by necessity exclude parameters that are not collected for those women.

For all cancers diagnosed, the tumor characteristics listed in section 4.2.3 will be reported, overall and divided by women eligible or not eligible for MRI, as well as for women invited vs. not invited to MRI, eligible women undergoing vs. not undergoing MRI.

5.5.4. We will calculate summary statistics for the radiological process measures described in 4.2.4.

5.5.5. We will calculate summary statistics for each of the questionnaire responses described in 4.2.5.

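### The allocation ratio varies over time with MRI capacity, but the primary analysis is one crude pooled difference and no period-stratified estimate is planned

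*Combined protocol and SAP*

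**What the plan says.** **Allocation.** The protocol's Study Type section states: "The number of women randomized to the MRI-group and the non-MRI group will be adapted to available MRI capacity over time". Its Sample Size section confirms that the ratio is not constant: "Given the variable randomization ratio, described above, we estimate that a slightly larger number of women have been included in the non-MRI group". SAP 5.7 assumes about 1:1 for the power statement, which is an overall figure and says nothing about single periods. Neither document describes blocking or stratifying the randomisation by period.

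**Primary analysis.** SAP 5.4 compares the composite endpoint between arms on the absolute scale. Of the difference it says: "It is estimated by plugging into the formula the observed proportions". The Wald interval uses arm totals only, and the optional relative-scale analysis is pooled in the same way.

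**Other analyses.** SAP 5.9 adds a per-protocol analysis and imputation of patient characteristics. SAP 5.10 concerns 423 eligible women who never reached randomisation. The regressions in SAP 5.5.3 list neither arm nor calendar period. Only SAP 5.5.1 looks at time: it summarises "the age and number of women not eligible for MRI, eligible and invited for MRI, women declined MRI and women undergoing MRI", and does so "for the entire study period, and how it changes over time". That is descriptive and gives no arm comparison by period.

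**The concern.** Randomisation makes the arms comparable among women allocated under the same ratio. Pooling women allocated under different ratios keeps that property only if the event risk does not move with the ratio. If later women have a lower risk and a larger share of them go to MRI, the MRI arm looks better for a reason unrelated to MRI. If either trend reverses, MRI looks worse. An overall ratio near 1:1 does not prevent this, because shares of 40% and then 60% also average to one half.

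Some sources of drift are controlled. There is one hospital, the MRI protocol is fixed, and the selection rule is fixed: "The specific AI tool and its settings will remain the same during the study". Others are not. Eligibility depends on recall decisions, since the protocol excludes "women recalled for diagnostic work-up in the current regular screening process". Detection of endpoint cancers depends on attendance at the next screening, which SAP 5.7 assumes to be 80%. Either could change between April 2021 and May 2023. At stake are the reported effect size and, if the true effect is small or absent, power and the one-sided error. The plan contains no analysis that would show whether this had happened.

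**Working it through.** **1. The plan's own figure.** SAP 5.7 claims at least 90% power but states no number per arm, and the March 2023 amendment gives no replacement target, so the figure cannot be strictly reproduced. With the original estimate of about 1,050 per arm, 28.6 per 1000 and 84% averted, the normal approximation with pooled variance gives 99.1%. It gives 98.1% with 95% MRI attendance, 97.1% with the 80% rescreening factor and 94.9% with both. Exactly 90% needs 592 to 853 per arm across these variants. The claim is consistent with its inputs, and the present point does not depend on it.

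**2. Bias of the crude difference (no-MRI minus MRI) with no MRI effect.**

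Bias = −Cov(MRI share, event rate) / [s(1 − s)], where s is the overall MRI share.

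For two equal periods with MRI share s₁ then 1 − s₁, this is (r₁ − r₂)(1 − 2s₁). It is zero if either the share or the rate is constant.

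**3. Assumptions (none of the period figures is in the documents).** 1,200 women in two equal periods, with MRI/no-MRI numbers as follows:

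- S: 270/330 then 300/300 (45% then 50%), closest to the slightly larger non-MRI group the protocol expects.
- A: 240/360 then 360/240 (40% then 60%).
- B: 200/400 then 400/200 (one third then two thirds), an outer bound.

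The rates are 28.6 × 1.1 = 31.46 and 28.6 × 0.9 = 25.74 (difference 5.72) or, as an outer bound, 38.1 and 19.1 (difference 19.07 unrounded). The planned difference is 28.6 × 0.84 = 24.0 per 1000, with no reduction for attendance or rescreening.

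**4. Numbers put in.**

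- No effect, ±10%: S 5.72 × (330/630 − 270/570) = 0.29; A 5.72 × 0.2 = 1.14; B 5.72 / 3 = 1.91 per 1000.
- No effect, rate halving: 0.96, 3.81 and 6.36 per 1000.
- Planned effect, A, rate falling: no-MRI 0.6 × 31.46 + 0.4 × 25.74 = 29.17; MRI 0.16 × (0.4 × 31.46 + 0.6 × 25.74) = 0.16 × 28.03 = 4.48; difference 24.7. Rate rising: 28.03 − 0.16 × 29.17 = 23.4.

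**5. Simulation** (200,000 runs per case, SAP 5.4 Wald interval; ranges cover a falling and a rising rate):

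| | S | A | B |
|---|---|---|---|
| ±10%, planned effect: mean estimate (true 24.0) | 23.9–24.2 | 23.4–24.7 | 22.9–25.1 |
| ±10%, planned effect: power | 94.4–94.8% | 92.9–94.9% | 92.1–95.3% |
| ±10%, no effect, rate falling: false-benefit tail (without drift) | 3.0% (2.8%) | 3.3% (2.5%) | 3.9% (2.5%) |
| Rate halving or doubling, planned effect: mean estimate | 23.5–24.6 | 21.8–26.2 | 20.3–27.7 |
| Rate halving, no effect: false-benefit tail | 3.5% | 5.8% | 9.5% |

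If MRI averts half as much (12.0 per 1000), case A with ±10% gives 11.1 to 12.9, with power of 25–33% against 29%. The bias does not depend on sample size, but the tail does. At 400, 600 and 1,000 per arm it is 3.1%, 3.3% and 3.6% (A, ±10%) and 7.8%, 9.5% and 13.5% (B, halving).

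**6. The stratified alternative.** A Mantel-Haenszel risk difference with Sato variance, stratified by period, has zero expected bias in these null cases. Each null tail is 2.2–2.8% over 400, 600 and 1,000 per arm. At the planned effect with 600 per arm its coverage is 93.4–95.4%, against 89.3–95.0% for the crude interval.

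**7. Are five blocks enough?** This check used 93 weekly batches from April 2021 to May 2023 without the summer pauses, and 1,200 women. Share and rate both changed linearly, with the rate going from 38.1 to 19.1. The crude null bias is 1.3 per 1000 (40% to 60%) or 2.1 (one third to two thirds). Five blocks leave about 5% of it, 0.06 to 0.10 per 1000.

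**The case against.** The case against acting is about materiality. Bias needs share and risk to move together, and the documents show neither drift nor period ratios. In case S with ±10% drift almost nothing changes. The larger figures need case A or B, which come from no passage, or an event rate that halves or doubles within about two years. Quoting one tail also looks worse than the two-sided test: with no effect and ±10% drift, the two-sided error is 5.1% (S), 5.1% (A) and 5.3% (B), and the biases of 0.3 to 1.9 per 1000 compare with a sampling standard deviation of 9.6. Under that mild drift the crude estimate has slightly lower root-mean-square error than the stratified one (A 9.7 against 9.8, B 9.8 against 10.2 per 1000). The half-year blocks are not matched to actual ratio changes. SAP 5.5.1 would show variation in the ratio roughly, and the SAP Preface allows exploratory analyses.

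Much of this stands. It limits severity and weakens the preference for stratification as the primary estimate. It does not remove the gap. An overall ratio does not bound swings within periods. With larger drift the two-sided error does rise: with 2,100 women and a twofold rate change it is 5.8%, 8.1% and 13.8% for shares of 45% to 55%, 40% to 60% and 33% to 67%. SAP 5.5.1 makes the MRI share only roughly recoverable. The protocol treats women invited for MRI as the MRI group ("we estimate that around 1050 women have been invited for MRI (and thus included in the MRI group"), and the 423 women never randomised must first be removed. Numbers randomised by arm and period, and events by period, are not explicitly planned. Under the Preface, a stratified estimate not specified before database lock would have to be labelled post hoc.

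**Conclusion.** The concern holds. The ratio varies by design, the primary estimate ignores this, and no planned analysis stratifies the arm comparison by period. The consequence is conditional. There is essentially no bias if the ratio is constant or drift is unrelated to it, and with mild drift the shift is about 1 per 1000 or less at the planned effect of 24.0. In the outer-bound case it reaches about 3.7 per 1000 either way (20.3 to 27.7). These sizes rest on assumed period ratios, drift and arm sizes, because the documents give none of them; the flow-chart figures were not available to check. This is a cheap improvement that should be made. It is not an error that invalidates the trial.

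**What to change.** In SAP 5.4, before outcomes are analysed, specify a Mantel-Haenszel risk difference (no-MRI minus MRI) with a Sato-variance 95% confidence interval, stratified by five fixed blocks of selection date: April–June 2021, July–December 2021, January–June 2022, July–December 2022 and January–May 2023. The June/July boundaries fall in the summer pause described in SAP 3.2. Use one merge rule based on date and arm only: a block with no women in one arm joins the following block, and the last block joins the preceding one. Make this the primary estimate with the crude difference as a sensitivity analysis or, at the least, make it a pre-specified sensitivity analysis to the crude estimate. In either case, tabulate women randomised and primary events by arm and block.

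The cost is SAP wording, a few lines of code and one table. The estimate needs only selection date and arm; the protocol's Data collection methods section says randomisation is recorded. If the stratified estimate is primary, the power cost at the planned effect without drift, with 600 per arm, is:

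- five blocks: 0.1 points at a constant ratio, 0.5 if the share rises from 40% to 60% (93.9% to 93.4%), and 1.3 from one third to two thirds (93.8% to 92.5%);
- two sharp periods: 0.2 (S), 0.8 (A) and 2.8 (B) points.

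In the two-period cases the cost is 1.9 (A) and 5.8 (B) points at 400 per arm, and 0.2 and 0.5 at 1,000. The sensitivity-analysis version costs no power.
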